## **2.3 Patient disposition, demographics and other baseline characteristics**

### **2.3.1 Patient disposition**

The number of patients will be summarized by region (i.e., Eastern Europe, Western Europe, India, Japan, Asia (other than India and Japan), rest of world), country and treatment group for the RAN set. Further, for each study epoch (i.e., screening, run-in, treatment phase, post treatment follow-up), the overall number of patients who entered, completed, and discontinued that phase will be summarized including the reasons for discontinuation.

Time to premature treatment discontinuation will be displayed graphically for each treatment group using a Kaplan-Meier curve for the safety analysis set. The date of premature treatment discontinuation is defined as the date of last dose of study treatment. Patients who completed the study treatment will be censored at the date of last dose of study treatment.

Number of patients with protocol deviations will be tabulated by deviation category (e.g., selection criteria not met, prohibited concomitant medication).

The number of patients included in each analysis set will be tabulated, as well as the reasons for exclusions from analysis sets.

### **2.3.2 Patient demographics and baseline characteristics**

Demographic and baseline characteristics measured before randomization including age, gender, race, ethnicity, height, weight, BMI, relevant medical history, Screening spirometry parameters: (FEV1, FVC, FEV1/FVC and FEF25-75), FEV1 reversibility, percentage of predicted FEV1, duration of asthma, history of asthma exacerbations, smoking history, prior asthma treatment (ICS low dose, ICS/LABA low dose and in case of protocol deviation ICS other than low dose, ICS/LABA other than low dose will be included), prior concurrent medications (asthma-related and non-asthma related) baseline ACQ-7, [REDACTED] will be summarized by treatment group using the RAN set.

Continuous variables will be summarized using descriptive statistics (number of non-missing data, mean, standard deviation, median, first and third quartiles, minimum, and maximum) and categorical variables will be summarized in terms of the number and percentage of patients in each category including a category for missing data if any.

No statistical analyses will be provided for baseline comparability among the treatment groups.

In addition, the following categorizations of continuous variables will be done:

- Age into 12 - 17 years, 18 - 64 years, and  $\geq 65$  years;
- BMI into  $\leq 30.0$  kg/m^2 and  $> 30.0$  kg/m^2;
- Duration of asthma into  $< 1$  year, 1 - 5 years,  $> 5 - 10$  years,  $> 10 - 15$  years,  $> 15 - 20$  years, and  $> 20$  years;
- Number of asthma exacerbations in the 12 months prior to the start of the study that required treatment into 0, 1,  $> 1$
- pre-bronchodilator FEV1 into  $< 60\%$ ,  $60 - < 70\%$ ,  $70\% - < 90\%$ , and  $\geq 90\%$  of predicted FEV1 ( $< 60\%$  and  $\geq 90\%$  will be included in case of protocol deviation)
- ACQ-7 into  $< 1.5$ ,  $1.5 - < 2$ ,  $2 - < 2.5$ ,  $\geq 2.5$  ( $< 1.5$  will be included in case of protocol deviation)

Medical history will be coded with the Medical Dictionary for Regulatory Activities terminology (MedDRA) using the most recent version at the time of database lock. History/conditions will be summarized for the RAN set by primary system organ class and preferred term. Verbatim recorded history/conditions will be listed together with the coded terms, date of diagnosis/surgery and whether the problem was ongoing at start of the study.

## **2.4 Treatments (study treatment, rescue medication, concomitant therapies, compliance)**

### **2.4.1 Study treatment / compliance**

#### **2.4.1.1 Duration of exposure**

Duration of exposure to study treatment will be calculated as the number of days starting from the first dose date up to and inclusive the last dose date. The duration of exposure will be summarized by treatment for the safety set as a continuous variable with the standard descriptive statistics. In addition, the duration of exposure will be summarized with total patient years and the number (%) of patients who were exposed to study treatment for each 1 – 29 days, 30 – 85 days and  $> 85$  days.

The number of patients who completed the 12-week study treatment and who discontinued the study treatment prematurely will be shown including the reasons for discontinuation of study treatment.

#### **2.4.1.2 Compliance**

Compliance will be calculated by counting the days where study treatment was administered "As per protocol" according to the records on the Dosage Administration Record (DAR)

Summary eCRF. The percentage of days divided by the days of exposure will be analyzed. To be counted as a day of compliance with study treatment, two administrations, i.e., the Twisthaler and the Concept 1 inhaler in the evening, have to be taken as per protocol.

Compliance will be categorized into < 80 % and 80 % - 100 % and summarized by treatment for the safety set.

#### **2.4.2 Prior, concomitant and post therapies**

Each medication, either an asthma or non-asthma medication, will have the start and end dates recorded on the eCRF. Separate tables will be provided for medications which were started and stopped prior to the first dose of study treatment and medications which were taken concomitantly to the study treatment (regardless of whether continued or started after the first dose of study treatment).

Asthma medications will be summarized by the route of administration, the recorded prespecified drug subcategories (including types of combination) and the coded preferred terms. The summary will be repeated by showing ingredients instead of preferred terms. Non-asthma medications will be summarized by route of administration and preferred term.

Surgical and medical procedures (non-drug therapies) will be coded using MedDRA and presentations will be done by MedDRA primary system organ class and preferred term, separately for prior procedures and those after start of study treatment.

Short acting beta2 agonist (SABA) rescue medication usage (mean number of puffs) during the screening epoch will be summarized.

Patients taking prohibited concomitant medications will be noted in the summary of protocol deviations.

All summarizations will be by treatment group in the Safety Set.

### **2.5 Analysis of the primary objective**

#### **2.5.1 Primary endpoint**

The primary objective is to demonstrate the superiority of QMF149 150/80 µg to MF 200 µg in terms of trough FEV1 after 12 weeks of treatment.

Trough FEV1 is defined as the average of the two FEV1 measurements taken 23 hr 15 min and 23 hr 45 min post-evening dose. Trough measurements will be done at Day 2 and Day 85 (Week 12, the primary endpoint).

For trough FEV1, the baseline value is defined as the average of the values taken at -45 and -15 min prior to first dose of study treatment at the evening of Day 1. Checks will be performed to

ensure both values were indeed taken prior to the first dose of study treatment. If one of the -45 and -15 min values is missing (or is not confirmed to be pre-dose) then the remaining non-missing value will be taken as the baseline. If both values are missing (or not confirmed to be pre-dose), then the last out of the pre-bronchodilator measurements taken at the run-in Visits 101 and 102 or at unscheduled run-in visits will be used as the baseline. If the FEV1, FVC or FEF25-75 measurements are missing both on Day 1 and at run-in visits, the respective baseline values will be set to missing. Measurements taken within 6 hours of rescue use or within 7 days of systemic corticosteroid use will be set to missing.

For all spirometry measurements, implausible values will be excluded. If a patient has implausible FEV1 value (defined as > 7 L) at an assessment, all spirometry measurements related to that assessment will be excluded. The threshold of 7 L was chosen because according to ERS/ECCS 1993 regressions, the maximum normal predicted FEV1 is 5.17 L, we set 7 L as the implausible cutoff to allow for some fluctuation around the maximum mean.

## 2.5.2 Statistical hypothesis, model, and method of analysis

The comparison of QMF149 150/80 microgram versus MF 200 microgram will be evaluated by testing the following null hypothesis (H0) versus the alternative hypothesis (Ha):

H0: QMF149 treatment group is equal to MF treatment group in trough FEV1 at Week 12

Ha: QMF149 treatment group is not equal to MF treatment group in trough FEV1 at Week 12

The primary variable will be analyzed using a mixed model for repeated measure (MMRM) on the FAS. The model will contain treatment, age (12 to 17 or ≥ 18 years), region, visit (Days 2 and 85), and treatment-by-visit interaction as fixed effects with baseline FEV1 measurement, baseline-by-visit interaction, FEV1 prior to inhalation and FEV1 within 15 to 30 min post inhalation of salbutamol/albuterol (components of SABA reversibility) as covariates, and center nested within region as a random effect. The within-patient correlation will be modeled using an unstructured covariance matrix in the mixed model. The Kenward-Roger approximation will be used to estimate denominator degrees of freedom ([Kenward and Roger, 1997](#)). If the model does not converge, with unstructured covariance matrix, the compound symmetry covariance matrix will be used in the mixed model, if the model still does not converge the random effect will be removed, if the model converges after removing the random center effects, the original model without random center effects will be re-assessed. The restricted maximum likelihood method will be used. The between-treatment comparison will be carried out using the adjusted mean (least-squares mean (LS mean)) difference based on the treatment main effect and the coefficient for the treatment-by-visit interaction for Day 85 and treatment.

The estimated adjusted treatment difference (QMF149 – MF) will be displayed along with the associated standard error, 2-sided 95% confidence interval (CI), and p-value (2-sided).

## 2.5.3 Handling of missing values/censoring/discontinuations

If any of the 23 hr. 15 min and 23 hr. 45 min values contributing to the trough FEV1 is collected within 7 days of systemic corticosteroid use, within 6 hours of rescue medication, or if the actual

measurement times are outside the 22-25 hour post-evening dose time window then the individual FEV1 value will be set to missing.

If one of the two values is missing (or set to missing), then the remaining non -missing value will be taken as trough FEV1. If both values are missing, or if the patient withdrew from the study (regardless of the reason for discontinuation) then trough FEV1 will be regarded as missing in which case the missing value(s) of the patient at the particular visit(s) would not directly contribute to the primary analysis.

Post-dose spirometry measurements which were actually taken pre-dose will be set to missing and not used for by time point assessments. Similarly, any pre-dose spirometry measurements which were actually taken post-dose will be set to missing and not used for by time point assessments.

The MMRM which is used for the primary variable is based on missing at random mechanism for the missing values and assesses the treatment effects of trough FEV1 without explicit imputation.

#### **2.5.4 Supportive and Sensitivity analyses**

As supportive analysis, the same MMRM used in the primary analysis will be also performed on the PPS to assess the treatment effect in protocol adherers.

In addition, the same primary MMRM on the FAS will be performed including all spirometric measures irrespective of systemic corticosteroid or rescue medication use but those measures taken outside of the 22 – 25 hour post-evening dose time window will not be included.

As a sensitivity analysis, a so-called 'tipping point analysis' will be performed for the primary endpoint to evaluate the impact of a deviation from the MAR assumption of missing data. The delta-adjusting approach described in Ratitch et al (2013) will be used to find the tipping point, in a spectrum of conservative missing not at random (MNAR) assumptions, at which conclusions change from being favorable to QMF149 to being unfavorable. After such a tipping point is determined, clinical judgment can be applied as to the plausibility of the assumptions underlying this tipping point. This methodology would provide a good picture of what it would take to overturn study conclusions on the basis of varying assumptions about missing data. The basic idea is to first impute the missing values using a regression based multiple imputation (MI) method based on the MAR assumption. The imputed Week 12 values for the QMF149 arms are then adjusted by a delta value. A detailed description of the analysis steps are provided in [Section 6.6](#).

The exploratory subgroup analyses for trough FEV1 using MMRM will be performed (using the appropriate interaction term in the model and additional covariate as a fixed effect, if necessary) for the FAS population to explore the treatment effect in key demographic and disease related subgroups (See [Section 2.2.1](#) for the details of subgroups).

## 2.6 Analysis of the key secondary objective

### 2.6.1 Key secondary endpoint

The key secondary objective is to demonstrate the superiority of QMF149 150/80 µg to MF 200 µg in terms of ACQ-7 after 12 weeks of treatment.

The ACQ-7 measures asthma symptom control and consists of seven items: five on symptom assessment, one on rescue bronchodilator use and one on airway calibre (FEV1 % predicted). Patient recall is one week. All 7 questions of the ACQ-7 are equally weighted. Items 1-5 are scored along a 7-point response scale, where 0 = good controlled and 6 = poor controlled. Item 6 is scored between 0 = no rescue medication and 6 = More than 16 puffs/inhalations most days. The 7th item will be scored by the investigator based on the FEV1 % predicted from the masterscope at the site (i.e., Score = 0 means > 95% of predicted FEV1, 1 = 90 – 95%, 2 = 80 – 89%, 3 = 70 – 79%, 4 = 60 – 69%, 5 = 50 – 59%, and Score = 6 means < 50% of predicted FEV1). The total score is calculated as the mean of all questions. The mean will be calculated as the sum of scores divided by the number of questions that were answered, as long as there were at least 6 questions answered and the missing question is neither Question 1 ('On average, during the past week, how often were you woken by your asthma during the night?') nor Question 7. In case of one missing response (not Question 1 or Question 7), first that missing response will be imputed as per the method given in [Section 2.6.3](#) and then the ACQ score will be calculated.

ACQ-7 measurements are scheduled for Days -21, 1, 30 and 84.

For the ACQ-7 score, the baseline value is defined as the score obtained at Day 1 prior to first dose of study treatment. If the value is missing, the last measurements from run-in visit 101 or unscheduled run-in visits will be used.

### 2.6.2 Statistical hypothesis, model, and method of analysis

It will be analyzed using the same MMRM (including all available visits) on the FAS as used for the primary analysis but will include Baseline ACQ-7 score instead of Baseline FEV1.

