4.1 Inclusion criteria

Patients eligible for inclusion in this study must fulfill all of the following criteria:

- 1. Written informed consent must be obtained from all patients before any study-related assessment is performed. Patients below the legal age of consent are required to have the Parental Informed Consent signed by the patient's parent/legal guardian; adolescents are required to sign the Assent Form.
- 2. Male and female adolescents aged ≥ 12 to < 18 years old (depending upon regulatory and/or institutional Review Board (IRB)/Independent Ethics Committee (IEC)/REB approval and/or country participation) and male and female adults aged ≥ 18 years and ≤ 75 years old.
- 3. Patients with a documented diagnosis of asthma for a period of at least 3 months prior to Screening (Visit 1).
- 4. Patients who have used low dose ICS (Appendix 9), with or without another controller therapy (i.e., LABA, Leukotriene Receptor Antagonist (LTRA)) at stable dose for at least 1 month prior to Screening (Visit 1).
- 5. Adult patients must be symptomatic despite treatment with existing therapy. Patients must have ACQ-7 score ≥ 1.5 at Visit 101 and at Visit 102 (i.e., inadequately controlled).
- 6. Adolescent patients:
 - If taking low dose ICS (without LABA), patients must be symptomatic despite treatment with low doses of ICS. These patients must have ACQ-7 score \geq 1.5 at Visit 101 and at Visit 102 (i.e., inadequately controlled).
 - If taking low dose ICS / LABA, patients may be included only if ACQ-7 score ≥ 1 and <1.5 at Visit 101 (i.e., adequately controlled). However, ACQ-7 score must be ≥ 1.5 at Visit 102, directly prior to randomization.
- 7. Pre-bronchodilator $FEV_1 \ge 60\%$ and < 90% of the predicted normal value for the patient according to ATS/ERS criteria after withholding bronchodilators at both Visits 101 and 102.
 - Withholding period of bronchodilators prior to spirometry: SABA for ≥ 6 hours and FDC or free combinations of ICS/LABA* for ≥ 48 hours (14 days for once daily combinations, i.e., indacaterol), short acting anticholinergies (SAMA) for ≥ 8 hours, xanthines ≥ 7 days.

*In case of combination ICS/LABA, ICS should be continued.

Washout period of each drug should be kept as close as possible as above and should not be longer. If washout period is considered to be longer, please contact your Novartis Medical Monitor.

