#### 2.6.4 Multiplicity adjustment

A hierarchical testing procedure will be applied to control the type-I error rate for the primary and the key secondary endpoints, i.e., the key secondary endpoint ACQ-7 will be tested only if the primary endpoint (trough FEV1) is significant at the 2-sided 0.05 level.

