## **3 Sample size calculation**

The sample size calculation takes into account the following consideration:

1. To achieve at least 90% power for the primary endpoint trough FEV1 with a treatment difference of 100 mL between QMF149 vs. MF, assuming a standard deviation of 380 mL based on internal studies CQMF149A2210, CQMF149E2201, CQMF149E2203

and literature data, where most observed treatment effects range approximately 80 mL to 120 mL.

1. To achieve at least 75% power (with multiplicity adjustment) for the secondary endpoint ACQ-7 with a treatment difference of -0.18 between QMF149 vs. MF, assuming a standard deviation of 0.80 based on study CQMF149A2210, where observed treatment difference was -0.21 with 95% confidence interval (-0.28, -0.15);

If 10% dropout rate is assumed, then calculation shows the sample size of 750 patients (ie 375/arm) will provide approximately 93% power for item 1 and 77% power for item 2 with multiplicity adjustment.

The sample size calculation was performed in PASS software.

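### The key secondary ACQ-7 model is valid, but adding the Visit 101 ACQ-7 score as a second pre-randomisation covariate would be a cheap, probably modest gain in precision

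*SAP*

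**What the plan says.** SAP 2.6.1: "ACQ-7 measurements are scheduled for Days -21, 1, 30 and 84". Protocol Table 6-1 places Day -21 at Visit 101 and Day 1 at Visit 102, so there are two scores before randomisation. Both are eligibility criteria. For adults, Protocol 4.1 states: "Patients must have ACQ-7 score ≥ 1.5 at Visit 101 and at Visit 102". Adolescents also need qualifying scores at both visits, with a different Visit 101 range for those on ICS/LABA.

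SAP 2.6.2 takes the primary model "as used for the primary analysis but will include Baseline ACQ-7 score instead of Baseline" FEV1. Protocol 9.5 specifies the same model. The formula in SAP 6.6 has one baseline term with its by-visit interaction, age group, region, random centre, and FEV1 before and after salbutamol from the reversibility test, which Table 6-1 schedules at Visit 101. It has no Visit 101 ACQ-7 term. That score replaces a missing Day 1 score (SAP 2.6.1) and helps impute a missing Day 1 item (SAP 2.6.3).

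ACQ-7 is tested only if trough FEV1 "is significant at the 2-sided 0.05 level" (SAP 2.6.4). SAP Section 3 gives "approximately 93% power for item 1 and 77% power for item 2 with multiplicity adjustment".

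**The concern.** The ACQ-7 covariates are carried over from the FEV1 model with one substitution. The result keeps the Visit 101 FEV1 values but not the ACQ-7 score from the same visit, and the documents give no reason. One ACQ-7 score has a one-week recall and is a noisy measure of a patient's usual level of control. For most patients it is also cut off at 1.5 by the entry rule. A second score three weeks earlier would usually carry some further information about Week 12.

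At stake is some precision on the second, lower-powered confirmatory test. The validity of that test is not in question.

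**Working it through.** **Inputs** (SAP Section 3 unless stated)
- ACQ-7: "ACQ-7 with a treatment difference of -0.18 between QMF149 vs. MF", with a "standard deviation of 0.80 based on study CQMF149A2210".
- Trough FEV1: "treatment difference of 100 mL between QMF149 vs. MF, assuming a standard deviation of 380 mL".
- 375 per arm with 10% dropout: 375 × 0.9 = 337.5, taken as 338 per arm, the figure in SAP 1.1.
- Two-sided alpha 0.05 (SAP 2.6.4).
- Not in the documents: any correlation between ACQ-7 scores, and whether 0.80 is a raw SD or the SD after baseline adjustment.

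**Step 1: reproduce the stated power.** Normal approximation: SE = SD × √(2/n), power = Φ(difference/SE − 1.96).
- √(2/338) = 1/13.
- Trough FEV1: SE = 380/13 = 29.23 mL; 100/29.23 = 3.42; power 92.8% (stated 93%).
- ACQ-7 alone: SE = 0.80/13 = 0.0615; 0.18/0.0615 = 2.925; power 83.3%.
- Product, treating the two tests as independent: 0.928 × 0.833 = 77.3% (stated 77%).

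So the 77% includes the chance of passing the primary test. ACQ-7 on its own has 83.3%.

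**Step 2: effect of a second score.** Let r1 be the correlation of Day 1 with Week 12, r2 that of Visit 101 with Week 12, and rb that of Visit 101 with Day 1. Then

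R² with both scores = (r1² + r2² − 2·r1·r2·rb)/(1 − rb²),

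and residual variance is multiplied by v = (1 − R²)/(1 − r1²). There is no gain when r2 = r1 × rb.

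Examples with r1 = 0.5 and rb = 0.6 (assumed):
- r2 = 0.3: R² = 0.16/0.64 = 0.250; v = 0.750/0.75 = 1; no gain.
- r2 = 0.4: R² = 0.17/0.64 = 0.266; v = 0.734/0.75 = 0.979; 2.1% less variance.
- r2 = 0.5: R² = 0.20/0.64 = 0.3125; v = 0.6875/0.75 = 0.917; 8.3% less variance.

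A simulation keeping only patients with both scores at or above 1.5 (assumed correlations before selection 0.4 to 0.7, means 1.8 to 2.3, SDs 0.7 to 0.8) gave 1.3% to 8.3% less variance. This range is not a bound: without selection, all three correlations at 0.6 give 14.1%.

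**Step 3: power if 0.80 is the SD after Day 1 adjustment.** SE = 0.0615 × √v.

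| Variance saved (assumed) | SE | ACQ-7 alone | With multiplicity adjustment |
|---|---|---|---|
| 0% | 0.0615 | 83.3% | 77.3% |
| 2% | 0.0609 | 84.0% | 78.0% |
| 5% | 0.0600 | 85.1% | 79.0% |
| 8% | 0.0590 | 86.2% | 80.0% |

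**Step 4: power if 0.80 is a raw SD.** The planned one-baseline model has SD 0.80 × √(1 − r1²).

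| r1, r2, rb (assumed) | Planned, adjusted | With Visit 101 score | Gain (points) |
|---|---|---|---|
| 0.4, 0.3, 0.6 | 82.7% | 82.9% | 0.2 |
| 0.5, 0.4, 0.6 | 85.6% | 86.0% | 0.5 |
| 0.5, 0.5, 0.6 | 85.6% | 87.4% | 1.8 |
| 0.6, 0.6, 0.6 | 88.6% | 90.6% | 2.0 |

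(Gains are taken from unrounded powers.)

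**The case against.** The strongest reply is that this is a preference. The one-baseline model is valid, Protocol and SAP agree on it, and 77% already meets the stated target of at least 75%. All of that stands.

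A reader might infer that the planned analysis is in error, or that it certainly loses precision. The documents support neither. They give no ACQ-7 correlations, and the gain is zero if Visit 101 predicts Week 12 only through Day 1. Several features could weaken it:
- Visit 101 precedes the switch to run-in fluticasone, and its one-week recall can overlap twice-daily LABA use, which stops only 48 hours before the visit.
- Most patients are selected on both scores.
- Adolescents on ICS/LABA fall under a different Visit 101 range, which the simulation does not model; they are a subset of about 50 patients.
- The reversibility FEV1 values already carry part of ACQ-7 item 7.

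Nor is the Visit 101 score thrown away, since it serves eligibility, fallback and item imputation. The FEV1 model does not establish a rule of two baselines either: the SAP describes its Visit 101 terms as components of reversibility.

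It would also be too strong to say that the extra covariate can only help. An uninformative one costs degrees of freedom. A mixed model also drops patients with a missing covariate, so with a 1% variance saving, 1% missing Visit 101 scores would cancel the gain. Where Visit 101 already replaces a missing Day 1 score, the same value would enter twice. These points require explicit rules but do not defeat the change.

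**Conclusion.** A cheap improvement, not an error. The documents show that two ACQ-7 scores are taken before randomisation, that only the Day 1 score is a covariate, and that ACQ-7 is the lower-powered confirmatory test. Near-completeness of the Visit 101 score is inferred from its role in eligibility.

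The expected benefit is modest: 0 to about 2.7 points of multiplicity-adjusted power (77.3% to 80.0%) if 0.80 is a residual SD and 0 to 8% of residual variance is removed. If 0.80 is raw, planned adjusted power is already above 77%, and the gain was about 0.2 to 1.8 points for r1 of 0.4 or 0.5 and 2.0 points with all correlations at 0.6. These figures rest on assumed correlations, 338 completers per arm and independence of the two tests. If the score is uninformative, the loss is one to three degrees of freedom out of more than 600, which is negligible.

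**What to change.** Before unblinding:
- In SAP 2.6.2 and 6.6, add the Visit 101 ACQ-7 score and its by-visit interaction to the ACQ-7 mixed model, and add the score to the responder model and its imputation models. The Week 12 imputation step for ACQ-7 response in SAP 6.6 needs editing in any case, because it lists baseline FEV1 and not baseline ACQ-7.
- Keep Day 1 ACQ-7 as the reference for change from baseline and for response.
- State a rule for a missing Visit 101 score, for example single imputation from baseline data ignoring treatment, so that no patient is dropped.
- State a rule for patients whose Day 1 score is replaced by Visit 101, for example that the same value may stand in both terms.
- Record the departure from Protocol 9.5 in SAP Section 4, which now lists only the ACQ-5 analyses.

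A pooled check of the three correlations, blind to treatment, would show the likely size of the gain beforehand. The change needs no new data or visits. It costs one to three degrees of freedom and a documented change to a protocol-specified confirmatory model.
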